#### **9.4.3.2. Alcohol Consequences and Craving Scales**

The PACS is assessed weekly and will be analyzed similarly to the drinking endpoint (Section 9.4.3.1). PROMIS alcohol negative consequences scale is assessed at baseline and Study Week 7 which will be used for the secondary endpoint. Analysis of covariance will be used to analyze the PROMIS scale similarly to the primary endpoint (Section 9.4.1).

No imputation or multiplicity adjustment will be used for this endpoint.

#### **9.4.3.3. Smoking and Any Nicotine Use**

The mean number of cigarettes smoked in the past week is measured weekly. The sample is the mITT subjects who smoked at baseline. The data will be analyzed as described in Section 9.4.3. Covariates for this endpoint will be identified in Section 9.4.4. Amount of other nicotine products is not captured, only number of days of use of other nicotine products. The analysis of days of use in subjects using other nicotine products at baseline will use the same method as cigarettes smoked. In addition, 2 tables will examine the number of subjects that are abstinent from cigarettes and any nicotine product use. There will be one logistic regression, if there are sufficient number of subjects abstaining from nicotine use, with abstaining as the dependent variable and covariates as described in Section 9.4.4. No imputation will be used for these endpoints.

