**Table 1: Schedule of Assessments**

Study Phase	Screening	Treatment					End of Study a	Follow-up Call
Clinic Visit #	1	2	3	4	5	6	7	
Study Week (Days) b	-2 to -1 (-14 to -1)	1 (1 to 7)	2 (8 to 14)	3 (15 to 21)	4 (22 to 28)	5 (29 to 35)	7 (43 to 49)	9 (57 to 63)
Informed Consent	X							
Alcohol Breathalyzer	X	X	X	X	X	X	X	
Urine Drug Test c	X	X	X	X	X	X	X	
Locator Form	X	Update	Update	Update	Update	Update	Update	
Demographics	X							
Medical History	X	Update						
Physical Exam	X	Update						
Body Weight	X				X		X	
MINI	X							
C-SSRS		X	X	X	X	X	X	
Clinical Chemistry d	X				X		X	
Hematology e	X				X		X	
Medical Urinalysis f	X				X		X	
Pregnancy Test	X	X					X	
Birth control methods (all subjects)	X	Update	Update	Update	Update	Update	Update	

Study Phase	Screening	Treatment					End of Study a	Follow-up Call
Clinic Visit #	1	2	3	4	5	6	7	
Study Week (Days) b	-2 to -1 (-14 to -1)	1 (1 to 7)	2 (8 to 14)	3 (15 to 21)	4 (22 to 28)	5 (29 to 35)	7 (43 to 49)	9 (57 to 63)
Vital Signs g	X	X	X	X	X	X	X	
Eligibility Checklist	X	X						
Drinking Goal	X							
ECG	X				X		X	
Prior and Concomitant Meds	X	X	X	X	X	X	X	X
CIWA-AR	X	X	X	X	X	X	X	X
Screening Cue Reactivity Session: VAS Scales	X							
Randomization		X (Day 1)						
Blood for Drug Concentration					X		X	
Drug compliance/ accountability/ Review AiCure		Dispense Day 1	X	X	X	X	X	
AEs (open ended question)		X	X	X	X	X	X	X
Brief Telephone Interview h		once during the week	once during the week	As needed if the subject misses a clinic visit				
Take Control		X	X	X	X i	X	X	
Treatment Cue Reactivity Session: VAS Scales				X				

Study Phase	Screening	Treatment					End of Study a	Follow-up Call
Clinic Visit #	1	2	3	4	5	6	7	
Study Week (Days) b	-2 to -1 (-14 to -1)	1 (1 to 7)	2 (8 to 14)	3 (15 to 21)	4 (22 to 28)	5 (29 to 35)	7 (43 to 49)	9 (57 to 63)
TLFB	X	X	X	X	X	X	X	
Brief Drinking Questionnaire	as needed							
Exit Interview							X	
ACQ-SF-R	2X pre/post cue session			2X pre/post cue session				
PACS		X	X	X	X	X	X	
Cigarette smoking quantity/frequency and nicotine use		X				X	X	
PSQI		X				X	X	
POMS		X				X	X	
PROMIS Alcohol Negative Consequences		X					X	
Hyperkatifeia Scale		X						
Treatment Referral							X	
Follow-Up Telephone Interview								X
Final Subject Disposition								X

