### **5.3. Alcohol-Related Craving, Consequences, and Withdrawal**

Alcohol-related craving is measured using the ACQ-SF-R scale and PACS; alcohol-related consequences are measured using the PROMIS Alcohol Negative Consequences scale; and alcohol-related withdrawal is measured using the CIWA-AR scale. The PACS and PROMIS

Alcohol Negative Consequences are used as efficacy endpoints, while the ACQ-SF-R and CIWA-AR scales are safety endpoints.

The ACQ-SF-R contains 12-items adapted from the 47-item ACQ-NOW developed by [Singleton et al \(1994\)](#) to assess craving for alcohol among alcohol users in the current context (right now). Items 3, 8, and 11 are reverse keyed. A general craving index is derived by summing all items and dividing by 12. If an item is missing, then the number of items is reduced by the number missing, and the sum is only the sum of the answered items. At least 10 items must be endorsed for the general craving index of ACQ-SF-R to be considered non-missing (i.e., scored).

The PACS is a five-item self-administered instrument for assessing craving ([Flannery-1999](#)). Frequency, intensity, and duration of thoughts about drinking are assessed along with ability to resist drinking. The final item asks the responder to provide an average rating of his/her craving over the course of the past week. The questions on the PACS use descriptors coupled with numerical ratings ranging from 0 to 6. The items are summed for a total score.

PROMIS Alcohol Negative Consequences scale is for negative consequences from alcohol use. The short form of the PROMIS Alcohol Negative Consequences questionnaire will be used to assess outcomes of alcohol use over the past 30 days ([Pilkonis-2013](#)).

The 7 PROMIS items include:

- Drinking created problems between me and others
- I disappointed others when I drank
- I was unreliable after I drank
- Others complained about my drinking
- I used poor judgment when I drank
- I said or did embarrassing things when I drank
- I had trouble getting things done after I drank

Each item is rated on a 5 point scale including: Never (1), Rarely (2), Sometimes (3), Often (4), and Almost Always (5) for the past 30 days. A subject's total score is converted to a T-score using scoring table provided by NIH PROMIS.

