## **5.6. Cigarette Smoking Quantity-Frequency and Nicotine Use Questionnaire**

A smoking quantity frequency and nicotine use interview will include 3 questions to assess nicotine use via cigarette smoking or via other products during the study: 1) Over the past week, on how many days did you smoke cigarettes?; 2) On the days you smoked during the past week, how many cigarettes did you smoke on average?; and 3) Over the past week, on how many days did you use other nicotine products (ex. chew, cigars, cigarellos, e-cigarettes, vape, gum, patch, etc...)? At baseline subjects that answer “0” to question #1 are considered non-smokers for the study. Cigarettes per week is the answer to question #1 multiplied by the answer to question #2. At baseline, subjects who report smoking (question #1) or the use of other nicotine product (question #3) will be considered nicotine users. The responses to questions #1 and #3 will be

used to calculate the percentage of subjects abstinent from nicotine use among nicotine users. No imputation for missing values will be used.

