### **9.4.3. Analysis of the Secondary Efficacy Endpoints**

Secondary efficacy endpoints will also be analyzed based on data collected during the last 4 weeks of the maintenance period (Weeks 3 through 6), including TLFB and other questionnaire data assessed at Week 7 that reflect data collected during this period. Note that the data collected at Week 7 reflect drinking and other questionnaire items that occurred during Week 6.

In general, every continuous secondary efficacy endpoint is analyzed using a repeated measures mixed effects model where subjects are random effects; factors and covariates are fixed effects. The analyses will be performed using SAS PROC MIXED procedure. The information criterion is requested from every mixed effects model. Subjects are treated as a class variable and not continuous. The week (Weeks 3 through 6), treatment group, and clinical site are also treated as class variables.

The primary analysis model for all continuous endpoints is:

- Appropriately transformed endpoint = treatment + week + treatment\*week + clinical site + baseline equivalent of endpoint + other covariates (identified in Section 9.4.4)

This model will also be created for the untransformed endpoint. The solution statement from SAS PROC MIXED is requested to provide the solution for the fixed effects parameters. A

REPEATED statement specifies that values are repeated each week and subjects are nested within treatment group. The covariance structure is specified.

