**Table 85: Mean Cigarettes Smoked Among Smokers (mITT) – Full Model, Mixed Effects, Weeks 3-6**

**Table 86: PACS (mITT) – Weeks 3-6**

**Table 87: PACS (mITT) – Full Model, Mixed Effects, Weeks 3-6**

**Table 88: Percentage of Subjects Abstinent from Nicotine Use Weeks 3-6 – Among Subjects that Used Nicotine Products at Baseline**

	ASP8062	Placebo	Total
	(N=xx)	(N=xx)	(N=xxx)
No Nicotine Use			
Yes	xx (xx.x%)	xx (xx.x%)	xx (xx.x%)
No	xx (xx.x%)	xx (xx.x%)	xx (xx.x%)

 Nicotine use includes cigarettes or other nicotine products

**Table 89: Percentage of Subjects Abstinent from Nicotine Use Weeks 3-6 – Full Model Logistic Regression (Among Nicotine Users at Baseline)**

									95% CI 	
Parameter		DF 	Estimate	Standard Error	Wald Chi-Square	Pr > Chi-Square	Cohen's h	OR 	Upper CI	Lower CI
Intercept		1	xx.XXX	xx.XXX	xx.XXX	0.XXX				
Treatment	Overall	x	xx.XXX	xx.XXX	xx.XXX	0.XXX				

									95% CI 	
Parameter		DF 	Estimate	Standard Error	Wald Chi-Square	Pr > Chi-Square	Cohen's h	OR 	Upper CI	Lower CI
Treatment 	ASP8062	x	xx.xxx	xx.xxx	xx.xxx	0.xxx	0.xxx	xx.xxx	xx.xxx	xx.xxx
Site	Overall	x	xx.xxx	xx.xxx	xx.xxx	0.xxx				
Site 	1	x	xx.xxx	xx.xxx	xx.xxx	0.xxx		xx.xxx	xx.xxx	xx.xxx
Site	2	x	xx.xxx	xx.xxx	xx.xxx	0.xxx		xx.xxx	xx.xxx	xx.xxx
Cov		x	xx.xxx	xx.xxx	xx.xxx	0.xxx		xx.xxx	xx.xxx	xx.xxx

 Nicotine use includes either cigarettes or other nicotine products;  DF is degrees of freedom;  OR is odds ratio;  CI is confidence interval;  Comparison to placebo for each active treatment;  Site 3 is reference for the OR

*Programming note: COV is baseline equivalent of dependent variable and any other covariate(s) which have not been specified at the time of writing of SAP*

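### Cigarette and nicotine endpoints are planned as Weeks 3-6 data, but the schedule collects them only at Weeks 5 and 7, so four-week nicotine abstinence rests on at most 14 of 28 days

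*SAP*

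**What the plan says.** SAP 9.4.3.3 says "The mean number of cigarettes smoked in the past week is measured weekly" and analyses cigarettes by the Section 9.4.3 mixed model, in which week (3 to 6) is a class variable. Days of other nicotine use follow the same method. The same section plans tables of abstinence from cigarettes and from any nicotine, and a logistic regression if enough subjects abstain.

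The shells follow that text. Table 85 is titled "Mean Cigarettes Smoked Among Smokers (mITT) – Full Model, Mixed Effects, Weeks 3-6" and takes Table 75 as its template, with least squares means at Weeks 3, 4, 5, 6 and overall. Tables 88-91 report nicotine and smoking abstinence for Weeks 3-6. Figure 11 plots weekly cigarettes over the entire treatment period.

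The Schedule of Assessments (SAP Section 3.2, Table 1) differs. The row "Cigarette smoking quantity/frequency and nicotine use" is marked at Weeks 1, 5 and 7 only. SAP 5.6 gives the recall period: "Over the past week, on how many days did you smoke cigarettes" and "Over the past week, on how many days did you use other nicotine products".

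**The concern.** The analysis text and the schedule describe different data. A programmer following SAP 9.4.3.3 will find no Week 3 or Week 4 smoking records. If the software drops the empty levels, the overall cigarette estimate becomes a two-visit average under a Weeks 3-6 title.

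The abstinence tables are the more serious case, because the result is a single yes or no per subject and gives no sign of which days were asked about. A report of four-week nicotine abstinence would rest on half of the period at best. These are secondary endpoints 10 and 11, and 11 is also a protocol endpoint, to be analysed over the last four weeks of treatment.

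**Working it through.** **1. Is the schedule read correctly?** PSQI and POMS carry the same marks (Weeks 1, 5 and 7). The SAP shells model both at Weeks 5 and 7 (Tables 93 and 95), and the descriptive PSQI table has rows 1, 5 and 7. The reading is therefore sound and not a damaged table.

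**2. Does anything fill the gap?** The scheduled Week 1 and Week 2 telephone calls collect adverse events, concomitant medication and CIWA-AR, and give a compliance reminder (Schedule footnote h). They do not collect smoking. SAP 5.6, 9.4.3.3 and 9.5 rule out imputation.

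**3. Degrees of freedom.**
- Planned: Weeks 3, 4, 5, 6 give Week DF = 4 - 1 = 3, which reproduces the figure in Table 75.
- Planned Arm*Week DF = (2 - 1) × (4 - 1) = 3. Table 75 prints 5, a separate slip in the template.
- With the data scheduled (Week 5, and Week 7 standing for Week 6): Week DF = 2 - 1 = 1 and Arm*Week DF = (2 - 1) × (2 - 1) = 1.
- If all four levels are kept, the treatment + week + treatment*week design has 8 columns but rank 4. Means and contrasts at Weeks 3 and 4 are not estimable.

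**4. Days observed.** Weeks 3-6 are Days 15-42, which is 28 days. The visit windows are Days 29-35 (Week 5) and Days 43-49 (Week 7). Take recall as the seven days before the visit day.
- Week 5: a Day 29 visit covers Days 22-28 and a Day 35 visit covers Days 28-34. All 7 days lie inside Days 15-42.
- Week 7: a Day 43 visit covers Days 36-42 (7 days inside) and a Day 49 visit covers Days 42-48 (1 day inside).
- Total: 7 + 1 = 8 to 7 + 7 = 14 days. The maximum is 14/28 = 50%.
- If recall includes the visit day, Week 7 contributes 0 to 6 days and the total is 7 to 13.
- With one assessment missing, at most 7 days (25%) are observed.

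The earliest day any on-treatment smoking recall can reach is Day 22, so Week 3 (Days 15-21) is never observed. A subject who used nicotine only in that week would count as abstinent for Weeks 3-6.

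**5. Missing-assessment rule.** SAP 5.6 says which questions define abstinence, but no section says how many assessments are needed to classify a subject.

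**The case against.** Four counter-arguments deserve weight.

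- **The model still runs.** A reader might infer that it cannot be fitted. Class levels come from the data, so with two observed weeks it runs and the treatment effect is estimable. What is lost is the Week 3 and Week 4 estimates and the accuracy of the titles. This objection stands.
- **No bias is shown.** A reader might infer that abstinence will be badly inflated. The documents give neither weekly nicotine-free rates nor persistence, so any size is assumed. With independent weeks and a 0.7 nicotine-free probability, 0.7² = 0.49 would be scored against a true 0.7⁴ = 0.24. With 30% nicotine-free in any week and 95% remaining so from one week to the next, the figures are 0.271 and 0.257. A gap of 25 points or of about 1 point is equally compatible with the documents. The same recall windows apply to both arms. The objection stands as to size, but not as to the label.
- **PACS might seem to share the fault.** SAP 9.4.3.2 says "The PACS is assessed weekly and will be analyzed similarly to the drinking endpoint", yet there is no Week 6 visit. PACS is, however, scheduled at Weeks 3, 4, 5 and 7, and SAP 9.4.3 adds: "Note that the data collected at Week 7 reflect drinking and other questionnaire items that occurred during Week 6". All four levels therefore have data. Nor does the Week 3 PACS simply describe Week 2. That visit may fall anywhere in Days 15-21, and SAP 5.3 states a past-week period only for the final item ("average rating of his/her craving over the course of the past week"). PACS is not part of this point.
- **Perhaps the schedule is the error.** The protocol synopsis lists smoking assessment during treatment without a frequency. That is why the fix begins with reconciliation.

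**Conclusion.** The plan is wrong as written for cigarettes, days of other nicotine use, and nicotine and smoking abstinence. The cigarette model has two of its four weeks. Abstinence for Weeks 3-6 rests on at most 14 of 28 days, and on 7 to 14 across the permitted visit days and both readings of the recall period, when both assessments are present. This assumes that the schedule is followed as printed and that each answer covers seven days.

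The reach is limited: two of 15 secondary endpoints, in subsets of smokers and nicotine users. The primary endpoint is untouched.

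One note on the Week 7 visit. Equating its data with Week 6 is exact for past-week items only at Day 43, if Day 42 is the last treatment day. A visit on Days 44-49 recalls 1 to 6 post-treatment days. Reporting the visit day is enough.

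**What to change.** Reconcile SAP 9.4.3.3 with the Schedule of Assessments. If weekly collection was intended, the schedule must show it and the data must actually be collected.

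If the schedule stands:
- State in SAP 9.4.3.3 that smoking and nicotine use are assessed at Weeks 5 and 7 after baseline, as for PSQI and POMS.
- Fit the cigarette and other-nicotine models with those two time levels. Correct the degrees of freedom, rows and titles of Tables 84-85, and the content and title of Figure 11.
- Relabel Tables 88 and 89, and endpoint 11 in the SAP and the protocol, as no nicotine use reported in the past week at both the Week 5 and Week 7 assessments. Relabel Tables 90 and 91 the same way for smoking.
- State in advance how a subject with only one assessment is classified.
- Report the day of the Week 7 visit for the past-week items.

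No new data are needed. The cost is SAP text, table and figure shells, and a change of endpoint label in the protocol. The drawback is that the nicotine endpoint claims less than four weeks of abstinence, which is all that the scheduled data can support.

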#### **9.4.3.4. Sleep and Mood Scales**

The PSQI total score, POMS 6 subscales and total disturbance score are continuous variables. The data will be analyzed as described in Section 9.4.3. Covariates for these models will be identified as in Section 9.4.4.

No imputation or multiplicity adjustment will be used for these endpoints.

### **9.4.4. Covariate Adjustment for the Analysis of Secondary Efficacy Endpoints**

Covariates for continuous secondary efficacy endpoints include the baseline equivalent of the endpoint, clinical site, treatment, time and the treatment by time interaction. Additional covariates for the secondary efficacy endpoints may include baseline characteristics with a theoretical and/or empirical basis for a relationship with a particular secondary endpoint. Such characteristics may include, but are not limited to, drinking goal (stop drinking versus reduce drinking but not stop), age, and baseline alcohol craving scale total score. Prior to the unblinding of the data, matrices of correlations between these baseline characteristics and each of the secondary efficacy endpoints, pooled across blinded treatment assignment, will be produced (using Pearson for continuous variables, Spearman for categorical outcomes). Selection of baseline variables to include as covariates in the models will be based on consideration of the following criteria: at least modest correlation with outcome (i.e.,  $r \geq 0.20$ ) and clinical expertise. Each endpoint may have a unique set of covariates. Care is taken to only select a limited number of covariates such that the models are not over fitted.

Covariates for the dichotomous secondary endpoints, percentage of subjects abstinent, WHO 1-level risk category decrease, and WHO 2-level risk category decrease in alcohol consumption, will use phi correlation with dichotomous variables, chi-square statistic for categorical variables, and biserial correlation. Fewer covariates for the logistic regression may be used depending upon the number of events. If the number of events permits the inclusion of a baseline drinking covariate, the percentage of days abstinent will be used as the covariate for the percent subjects abstinent endpoint and the percent heavy drinking days will be used as the covariate for the percent subjects with no heavy drinking days endpoint; however, no baseline drinking covariate will be employed for the endpoint, percent subjects with a WHO decrease in alcohol consumption, as this endpoint already adjusts for baseline drinking in its calculation.

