
Number of Subjects (Planned): 60
Main Inclusion/Exclusion Criteria: Subjects will be male and female at least 21 years of age with 4 or more DSM-5™ symptoms of AUD (moderate to severe AUD). They must also be seeking treatment for AUD and if male, report drinking an average of at least 28 drinks per week or if female report drinking an average of at least 21 drinks per week prior to consent, and have at least 1 heavy drinking day (4 or more drinks per day for women/5 or more drinks per day for men) during the 7-day period prior to randomization.
Investigational Product, Dosage and Mode of Administration: The target doses are 25 mg tablet of ASP8062 by oral administration once daily at bedtime for 6 weeks.
Reference Therapy, Dosage and Mode of Administration: Subjects in the placebo group will take an equivalent number of identically matched placebo tablets (one per day) by oral administration once daily at bedtime for 6 weeks.
Duration of Study: Each subject will participate in the study for up to 11 weeks, including up to 2 weeks of screening, 6 weeks of treatment, one end-of-study visit during the week following the last treatment dose, and a final telephone contact ~2 weeks after completing treatment for a safety follow-up.

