### **5.2.8. World Health Organization Drinking Risk Categorical Scale**

The WHO has developed a drinking risk categorical scale that can be used in a responder analysis approach to assess clinically relevant decreases in alcohol consumption ([Aubin et al-2015](#)). Two dichotomous endpoints will be analyzed: WHO 1-level and WHO 2-level decrease in alcohol consumption. The WHO 1-level and 2-level decrease endpoints are the percentage of subjects experiencing at least a 1-level or 2-level decrease in WHO levels of alcohol consumption, respectively, from the level at baseline (the period including the 28 days before screening) to the level during the last 4 weeks of the maintenance phase (Study Weeks 2-5). The WHO levels of average alcohol consumption per day are as follows:

	Males	Females
Low Risk	1 to 40g	1 to 20g
Medium Risk	41 to 60g	21 to 40g
High Risk	61 to 100g	41 to 60g
Very High Risk	101+g	61+g

where 14g = 1 SDU ([WHO-2000](#)). In computing the alcohol consumption level, average drinks per day will be used, computed as the sum of all drinking in the 28 day period divided by the number of days with non-missing drinking data in that period. Abstinent subjects will be included in a separate “Abstinent” category. A subject must have at least 1 week of data during the last 4 weeks of the maintenance phase to be considered non-missing.

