**Table 71: WHO 1-Level Decrease in Alcohol Consumption (mITT) – Full Model, Logistic Regression, Weeks 2-5**

									95% CI 	
Parameter		DF 	Estimate	Standard Error	Wald Chi-Square	Pr > Chi-Square	Cohen's h	OR 	Upper	Lower
Intercept		1	xx.XXX	xx.XXX	xx.XXX	0.xxx				
Treatment	Overall	X	xx.XXX	xx.XXX	xx.XXX	0.xxx				
Treatment 	ASP8062	X	xx.XXX	xx.XXX	xx.XXX	0.xxx	0.xxx	xx.XXX	xx.XXX	xx.XXX
Site	Overall	X	xx.XXX	xx.XXX	xx.XXX	0.xxx				
Site 	1	X	xx.XXX	xx.XXX	xx.XXX	0.xxx		xx.XXX	xx.XXX	xx.XXX
Site	2	X	xx.XXX	xx.XXX	xx.XXX	0.xxx		xx.XXX	xx.XXX	xx.XXX
Cov		X	xx.XXX	xx.XXX	xx.XXX	0.xxx		xx.XXX	xx.XXX	xx.XXX

 DF is degrees of freedom;  OR is odds ratio;  CI is confidence interval;  Comparison to placebo;

 Site 3 is reference for the OR

*Programming note: COV is baseline equivalent of dependent variable and any other covariate(s) which have not been specified at the time of writing of SAP*

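### SAP 9.4.4 keeps baseline drinking out of the WHO-decrease models because the endpoint is said to adjust for it already; it does not, and the cost is modest precision rather than bias

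*SAP*

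**What the plan says.** SAP 5.2.8 defines the two endpoints as a fall of at least one or two WHO risk levels, from the level in the 28 days before screening to the level in the last four weeks of treatment. The levels are sex-specific bands of mean grams per day, "where 14g = 1 SDU". It adds that "Abstinent subjects will be included in a separate" category.

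SAP 9.4.4 plans a baseline drinking covariate for the other two subject-level drinking endpoints (abstinence and no heavy drinking days) when the number of events permits. For the WHO endpoints it says "no baseline drinking covariate will be employed for the endpoint, percent subjects with a WHO decrease in alcohol consumption", and gives as its reason "as this endpoint already adjusts for baseline drinking in its calculation".

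Two other places differ. The programming note under SAP Table 71, the WHO 1-level logistic model, reads "COV is baseline equivalent of dependent variable and any other covariate(s) which have not been specified". Table 73, the 2-level model, is laid out as Table 71. The protocol synopsis, under the analysis of secondary endpoints, permits covariates for the dichotomous endpoints if there are enough events, and makes no exception for the WHO endpoints.

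**The concern.** Subtracting baseline, or counting levels from it, does not remove dependence on baseline. The bands are wide and the top one has no upper limit. Two people who cut down by the same proportion can therefore differ in outcome only because of where they began. If so, baseline intake is a prognostic variable for the WHO endpoints, and the stated ground for excluding it fails.

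With 30 subjects per arm, a chance difference between arms in very heavy drinkers would move the WHO result with no adjustment planned. The text and the shell also give a programmer two different models for the same table.

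**Working it through.** **Inputs from the documents.** The bands are in SAP 5.2.8. Men: Low 1–40, Medium 41–60, High 61–100, Very High 101+ g/day. Women: Low 1–20, Medium 21–40, High 41–60, Very High 61+. One drink is 14 g. For entry, men must "report drinking an average of at least 28 drinks per week" and women at least 21 (protocol, main inclusion criteria). There are 30 subjects per arm (SAP 7).

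**Not in the documents.** No baseline intake distribution, response rate, abstinence rate or power is given for the WHO endpoints, so there is no plan figure to reproduce. Steps 3 to 5 rest on assumptions.

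**Step 1: conversion.** g/day = drinks per week × 14/7. The entry floor is 28 × 2 = 56 g for men (Medium) and 21 × 2 = 42 g for women (High).

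**Step 2: reduction needed.** Reduction = 1 − U/b, where U is the upper limit of the target band and b is baseline g/day.

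| Baseline g/day | 1 level | 2 levels |
|---|---|---|
| Men 56 | 1 − 40/56 = 29% | abstinence, if it counts as a level |
| Men 62 | 1 − 60/62 = 3% | 1 − 40/62 = 35% |
| Men 100 | 1 − 60/100 = 40% | 1 − 40/100 = 60% |
| Men 102 | 1 − 100/102 = 2% | 1 − 60/102 = 41% |
| Men 200 | 1 − 100/200 = 50% | 1 − 60/200 = 70% |
| Men 280 | 1 − 100/280 = 64% | 1 − 60/280 = 79% |
| Women 42 | 1 − 40/42 = 5% | 1 − 20/42 = 52% |
| Women 62 | 1 − 60/62 = 3% | 1 − 40/62 = 35% |
| Women 200 | 1 − 60/200 = 70% | 1 − 40/200 = 80% |

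This step needs no distributional assumption, and it is enough to show that the stated reason is wrong.

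**Step 3: same proportional response at every intake.** Let m be the median reduction, s the log-SD and a the abstinent share. The chance of a 1-level drop is a + (1 − a)·Φ[(ln(U/b) − ln(1 − m))/s]. Take m = 35%, s = 0.4, a = 5%:

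- At 102 g: (−0.020 + 0.431)/0.4 = 1.03, so 0.05 + 0.95 × 0.848 = 0.86 (0.85 by simulation).
- At 200 g: (−0.693 + 0.431)/0.4 = −0.66, so 0.05 + 0.95 × 0.256 = 0.29.
- At 240 g: 0.18.

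Over six scenarios (m = 20%, 35% or 50%; s = 0.4 or 0.7; a = 5%), the chance in men was 0.63 to 0.96 at 102 g and 0.10 to 0.43 at 240 g. The gap within a scenario was 0.41 to 0.67.

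**Step 4: effect on the test, 30 per arm.**

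- 2-level endpoint, 60% men, m = 35%, s = 0.5, a = 5%, 1,500 trials; baseline terms were log intake, sex and a Very High indicator. Type I error was 3.9% without them and 4.1% with them. For an assumed log-ratio shift of 0.4, power was 52.8% and 53.4%, and the median odds ratio about 3.1 and 3.4.
- Men only, baseline log-normal with median 50 drinks/week and log-SD 0.5–0.6, truncated at 28, four scenarios, one log-intake term. Power changed by +1.2, +0.5, +3.8 and −0.4 points (1-level) and by +2.7, +1.4, +4.6 and +0.4 points (2-level).
- Further runs gave 58% to 64% (1-level) and 58% to 60% (2-level) in men and women, and +3.4 and +2.3 points in men. Type I error in the men-only runs was 5.1% without and 5.3% with the covariate (1-level), and 6.5% and 6.4% (2-level), so adjustment made no material difference.

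**Step 5: chance imbalance.** Suppose 6 of 30 against 2 of 30 subjects start above 200 g/day, a difference of 4/30 = 13.3 points. With a log-normal change (mean −0.5, SD 0.5), the 1-level chance in men is 75% at 101–140 g, 51% at 140–200 g and 22% above 200 g. The shift with no drug effect lies between 13.3 × 0.29 = 3.9 and 13.3 × 0.53 = 7.1 points, and is about 5 for the assumed mix. The standard error of a difference near 50% is √(2 × 0.25/30) = 12.9 points.

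**The case against.** The strongest reply is that nothing invalid happens. Allocation is randomised, so omitting a prognostic covariate leaves the test unbiased, and ordinary chance imbalance is already part of its error rate. A 6 v 2 split is unremarkable (Fisher p = 0.25), and its shift of about 5 points is well inside one standard error. The power gains are small, rest on assumed distributions, and concern two unpowered secondary endpoints among fifteen. All of this stands. A reader might infer from step 3 that the WHO comparison is biased or that its type I error is inflated. The documents do not support that, and the simulations show no such effect of the omission.

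A reader might also infer that a man at the entry floor can reach a 2-level drop only by abstaining. That assumes Abstinent counts as one level below Low. SAP 5.2.8 makes it a separate category but does not rank it. If it is not a level, such a man cannot reach the endpoint at all. The band concerned is narrow, 28 to 30 drinks per week (56–60 g).

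Other cover exists. Table 28 compares baseline drinking between arms, drinks per week is modelled with its baseline value, and drinking goal, age and craving remain eligible covariates for the WHO models. The Table 71 note also appears under Tables 67 and 89, so it is probably template text. That makes the conflict editorial, but it still has to be resolved. The protocol's wording is permissive, so the SAP narrows it rather than breaching an obligation.

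Finally, the dependence on baseline is saw-toothed and differs by sex, so one log-intake term captures only part of it. That limits the gain but does not support the SAP's reason. Too few events could justify leaving the covariate out. SAP 9.4.4 has that safeguard already, and it is not the reason given here.

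**Conclusion.** The point holds as a wrong rationale and an internal inconsistency, with modest consequences. The rationale fails on the SAP's own bands: the reduction a man needs for a 1-level drop runs from about 2% at 102 g/day to 50% at 200 and 64% at 280. The text of 9.4.4 and the Table 71 note cannot both be followed.

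The unadjusted test remains valid. What is lost is some precision, roughly 0 to 5 points of power; individual simulation results ran from −0.4 to about +6, all under assumed intake and response distributions. The unadjusted odds ratio is also nearer to 1 than the conditional one (about 3.1 against 3.4 in one scenario). That reflects a different estimand as much as a loss. No adjustment is made for chance imbalance in heavy drinkers at 30 per arm. The change is worth making because it is nearly free, not because the WHO results would otherwise be unsound.

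**What to change.** - Delete the clause in SAP 9.4.4 that excludes baseline drinking from the WHO models.
- Before unblinding, pre-specify one baseline drinking covariate for both WHO logistic models when events permit: log mean drinks per day over the 28 baseline days. Add sex or baseline WHO level only if the events allow.
- Make the notes to Tables 71 and 73 name that covariate. The baseline equivalent of a level drop is not otherwise defined.
- State in 5.2.8 whether Abstinent counts as one level below Low.

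The cost is SAP wording, one model degree of freedom, and an odds ratio that is conditional on baseline drinking and should be labelled so. The data are already collected.
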